07-Jun-2019	Before DB lock	Creation of amendment 1	
 • Tables added as required for ClinicalTrials.gov and EudraCT • Clarification of the definition of newly occurring or worsening • Region names have changed. • modified FAS population has been added • [REDACTED] • vitals signs and Friderica's correction have been removed from demographic summary • Analyses of prior and concomitant medications have partly been revised and described in more detail. Analyses regarding prohibited medications have been removed • Supplementary analyses regarding the primary endpoint have been reduced. The second supplementary analysis has been kept • Tipping point analysis has been removed. A sensitivity analysis on the modified full analysis set has been added. • Supplementary analyses of responders have been reduced. BPI-SF, PGIC, worst NRS, ISI will be summarized descriptively. • Temporal items of NPSI will not be summarized descriptively. No summaries of the 5 dimensions of NPSI during the treatment withdrawal period will be provided • Analyses of AEs have been reduced. No subgroup analyses and analyses of drug-related AEs will be provided • Dot plots and Kaplan Meier plots of AEs have been removed • Plot for liver function test have been removed 	
2.8.1 Adverse events 2.8.3 Laboratory data 2.8.4 Other safety data 1.1, Study design, [REDACTED] 2.2. Analysis sets [REDACTED] 2.2.3 Patient disposition, demographics and other baseline characteristics 2.4 Treatments (study treatment, rescue medication, concomitant therapies) 2.5 Analysis of primary objective 2.7 Analysis of secondary efficacy objective(s) 2.13 Other Exploratory analyses 2.8.1 Adverse events (AEs) 2.8.1.2 Liver events 2.8.3 Laboratory data

Date	Time point	Reason for update	Outcome for update	Section and title impacted (Current)
			
 Section has been removed. Summary statistics of laboratory parameters, vital signs and ECG intervals will not be presented Shift tables of laboratory data have been removed Bazett correction has been removed [REDACTED] 	2.8.4 Other safety data
			
 For derivation of exclusion windows PD date can not be used 	[REDACTED] 5.1.5 Prohibited medication for PDS

Table of contents

Table of contents	4
List of abbreviations	6
1 Introduction	9
1.1 Study design.....	9
1.2 Study objectives and endpoints	10
2 Statistical methods.....	11
2.1 Data analysis general information	11

DMC	Data Monitoring Committee
ECG	Electrocardiogram
eCRF	Electronic Case Report Form
ED ₅₀	The dose at which half of the maximum effect is reached
eGFR	Estimated Glomerular Filtration Rate
E _{max}	The maximum effect attributable to the drug
FAS	Full Analysis Set
FDA	Food and Drug Administration
GGT	gamma-glutamyltransferase
HIV	Human Immunodeficiency Virus
INR	International Normalized Ratio
IRT	Interactive Response Technology
ISI	Insomnia Severity Index
LFT	Liver function test
LoE	Lack of efficacy
MAR	Missing at random
mFAS	Modified Full Analysis Set
MCP-Mod	Multiple Comparison Procedure – Modelling
MDRD	Modification of Diet in Renal Disease
MedDRA	Medical dictionary for regulatory activities
NPSI	Neuropathic Pain Symptom Inventory
NRS	Numeric Rating Scale
NSAID	Nonsteroidal Anti-inflammatory Drugs
PCR	Protein-Creatinine Ratio

PHN	Post-Herpetic Neuralgia
PK	Pharmacokinetics
PGIC	Patient Global Impression of Change
PRO	Patient Reported Outcome
█	█
QTc	Corrected QT interval
QTcB	Bazett QT correction formula
QTcF	Fridericia QT correction formula
SAE	Serious Adverse Event
RDO	Retrieved drop-out
SAF	Safety population
█	█
SSRI	Selective Serotonin Reuptake Inhibitor
TBL	Total bilirubin
TD	Study Treatment Discontinuation
TEAE	Treatment-Emergent Adverse Events
ULN	Upper limit of Normal
USM	Urgent Safety Measures
VRS	Verbal Rating Scale
WHO	World Health Organization

Amendment 1

This amendment of the statistical analysis plan (SAP) is largely based on changes induced due to the early termination of the CEMA401A2201 study. 129 patients out of 360 planned patients have been randomized. As the number of patients included in the study is considerably reduced, an abbreviated Clinical Study Report (CSR) that still meets all requirements for reporting and disclosure of the demographics, primary endpoint, secondary endpoints and safety results to public registries will be created.

The primary analysis on the change from baseline to Week 12 in the weekly mean of the 24-hour average pain score will be performed as originally planned. Besides the primary estimand, which is of main clinical interest, the supplementary estimand, which provides insight into the magnitude of improvement in efficacy that might be achieved if all patients were able to take EMA401 as prescribed for 12 weeks, will be analysed. The other planned supplementary estimands will be dropped, as they are of minor interest in the situation with many study treatment discontinuations due to trial termination in the scope of the Urgent Safety Measures (USM).

To support the primary analysis and to get an idea about the effect that might be achieved if the trial had not been terminated and if all patients had the chance to complete the Week 12 assessment, a sensitivity analysis on a modified population will be performed. The modified full analysis set will include all patients who had a chance to complete the study before the termination date, i.e. who had been randomized at least 12 weeks before study termination date.

Due to the considerably reduced number of patients who completed the study, only descriptive subgroup analyses will be provided. Moreover, most of the secondary [REDACTED] endpoints will also be summarized descriptively only. [REDACTED]

1 Introduction

This statistical analysis plan (SAP) describes all planned analyses for the Clinical Study Report (CSR) of study CEMA401A2201, a Phase 2, double-blind, placebo-controlled, randomized dose ranging trial to determine the safety and efficacy of three dose levels of EMA401 in reducing 24-hour average pain intensity score in patients with post-herpetic neuralgia.

The content of this SAP is based on the final version of protocol CEMA401A2201 Amendment 1 (release date 14-May-2018). All decisions regarding final analysis, as defined in the SAP document, have been made prior to database lock and unblinding of the study data.

1.1 Study design

The study is interventional, randomized, parallel, placebo-controlled, dose ranging, double-blind treatment.

The study will consist of a Screening epoch (up to 5 weeks), a double-blind Treatment epoch (12 weeks), and a double-blind Treatment withdrawal epoch (1 week).

- In the initial cohort, patients will be randomized in a 1:1:1 ratio to treatment with placebo, EMA401 25 mg b.i.d., or EMA401 100 mg b.i.d. (approximately 135 patients). Randomization of patients to the high dose arm (EMA401 300 mg b.i.d.) will only be initiated following an unblinded safety review by an independent Data Monitoring Committee (DMC) after exposure of 50 patients treated with EMA401 up to 100 mg b.i.d. for at least 8 weeks (i.e. 25 patients on 25 mg b.i.d. and 25 patients on 100 mg b.i.d.).
- Future patients will then be randomized in the second cohort in a 1:1:1:2 ratio to treatment with placebo, EMA401 25 mg b.i.d., EMA401 100 mg b.i.d., or EMA401 300 mg b.i.d. (approximately 225 patients).

Overall approximately 360 patients were estimated to be enrolled in the study (i.e. approximately 90 patients were planned to be enrolled in each treatment arm). Due to the early termination in the scope of USM the EMA401 300 mg b.i.d. treatment arm was not initiated as planned. The original 1:1:1 randomization ratio has been applied to treatment with placebo, EMA401 25 mg b.i.d., or EMA401 100 mg b.i.d. At Week 12 (Visit 199), all patients who completed the 12-week double-blind Treatment epoch will enter the 1-week double-blind Treatment withdrawal epoch. The IRT system will indicate the unique medication number for the package of study drug to be dispensed to the patient during the double-blind Treatment withdrawal epoch. This medication number will correspond to the blinded withdrawal regimen assigned at Baseline.

[figure not shown]
Randomization will be stratified by region (e.g. America, Europe and Australia, Asia) and use of concomitant pain medication for PHN (yes/no) in order to achieve balance of treatment allocation within the stratification factors.

Primary objective of this study is to characterize dose-response for change in the weekly mean of 24-hour average pain intensity scores at Week 12.

1.2 Study objectives and endpoints

Table 1-1 Objectives and related endpoints

Objective(s)	Endpoint(s)

Primary Objective(s)
 
 To characterize dose-response for change in the weekly mean of 24-hour average pain intensity scores at Week 12 	
Endpoint(s) for primary objective(s)
 
 Dose-response in change in weekly mean of the 24-hour average pain score, using an 11-point Numeric Rating Scale (NRS), from Baseline to Week 12

Secondary Objective(s)
 
 To compare the efficacy of EMA401 vs. placebo in 24-hour average pain intensity score at Week 12, using an 11 point Numeric Rating Scale (NRS) by testing the superiority of at least one active dose of EMA401 vs. placebo To evaluate the efficacy of EMA401 compared to placebo, as measured by the Brief Pain Inventory-Short Form (BPI-SF) interference total score at Week 12 To evaluate the efficacy of EMA401 compared to placebo, as measured by the weekly mean of the 24-hour worst pain intensity score, using an 11-point Numeric Rating Scale (NRS) at Week 12 To evaluate the efficacy of EMA401 compared to placebo, on the Patient Global Impression of Change (PGIC) at Week 12 To evaluate the proportion of EMA401 patients achieving a $\geq 30\%$ and a $\geq 50\%$ reduction in weekly mean 24-hour average pain intensity score using the NRS compared to placebo (i.e., responder rates) at Week 12 To evaluate the effect of EMA401 compared to placebo on the Insomnia Severity Index (ISI) at Week 12 To evaluate the effect of EMA401 compared to placebo on the Neuropathic Pain Symptom Inventory (NPSI) at Week 12 To evaluate the safety and tolerability of EMA401 compared to placebo in PHN patients, as measured by treatment emergent adverse events (TEAEs), adverse events (AEs) leading to study 	
Endpoint(s) for secondary objective(s)
 
 Change in weekly mean 24-hour average pain score (using the 11 point NRS) from Baseline to Week 12 Change in BPI-SF interference total score from Baseline to Week 12 Change in weekly mean of the 24-hour worst pain score, using an 11-point NRS, from Baseline to Week 12 PGIC at Week 12 Proportion of patients meeting responder criteria from Baseline to Week 12 Change in ISI from Baseline to Week 12 Change in NPSI from Baseline to Week 12 Number and severity of treatment emergent adverse events and the frequency of adverse events leading to discontinuation. Number of serious adverse events.

Objective(s)	Endpoint(s)

drug discontinuation and serious adverse events (SAEs) throughout the study
 
 To evaluate the pharmacokinetics (PK) of EMA401 and exposure-response (decrease in pain intensity) relationship for EMA401 throughout the study 	
 Plasma pharmacokinetics of EMA401 will be characterized by population non-linear mixed effects modeling techniques
Exploratory Objective(s)	Endpoint(s) for exploratory objective(s)

 To evaluate the proportion of patients who need rescue medication and the time to first intake of rescue medication 	
 Proportion of patients who need rescue medication and the time to first intake of rescue medication 24-hour average NRS pain score by subgroup 

2 Statistical methods

2.1 Data analysis general information

The statistical analysis of the study will be performed by , a designated Contract Research Organization (CRO).

SAS version 9.4 will be used to perform all data analyses and to generate tables, figures and listings.

Qualitative data (e.g., gender, race, etc.) will be summarized by means of frequency tables; a missing category will be included as applicable. Percentages will be calculated using the number of patients in the relevant population or subgroup as the denominator.

Quantitative data (e.g., age, body weight, etc.) will be summarized by appropriate descriptive statistics, i.e., n, mean, standard deviation (SD), first quartile (Q1), median, third quartile (Q3), minimum, and maximum.

No interim analysis will be performed for the efficacy evaluation. An external Data Monitoring Committee (DMC) will be established with the primary goal to perform an ongoing review of safety data.

2.1.1 General definitions

Investigational drug and study treatment

The investigational drug, EMA401, will be provided as capsules. The following oral dosage strengths will be used: 12.5 mg, 50 mg.

All dosage strengths of EMA401 and placebo will be identical in appearance.

For all treatment groups, each dose will be self-administered orally as two capsules with a full glass of non-carbonated water twice daily, consisting of a morning dose and an evening dose.

The following abbreviated treatment groups, independently of cohort number, will be used as the headers in the tables for the double-blind Treatment epoch:

- Placebo b.i.d.
- EMA401 25 mg b.i.d.
- EMA401 100 mg b.i.d.

The following abbreviated treatment groups will be used as the headers in the tables for the double-blind Treatment withdrawal epoch:

- Placebo b.i.d. -> Placebo b.i.d.
- EMA401 25 mg b.i.d. -> EMA401 25 mg b.i.d.
- EMA401 25 mg b.i.d. -> Placebo b.i.d.
- EMA401 100 mg b.i.d. -> EMA401 100 mg b.i.d.
- EMA401 100 mg b.i.d. -> Placebo b.i.d.

Date of first and last administration of study drug

The date/time of first administration of study drug is defined as the first date/time of administration as per Dosage Administration Record eCRF. The date/time of last administration of study drug is defined as the last date/time when a dose is administered as per Dosage Administration Record eCRF. This value has to be compared to the "End of study treatment" as recorded on the corresponding eCRF. In case of different dates, the latest will be used as treatment end.

For subjects with missing first dose date, the randomization date will be considered as reference start date.

Study day

The study day, describes the day of the event or assessment date, relative to the reference start date which is the date of first administration of study drug.

The study day is defined as:

- The date of the event (visit date, onset date of an event, assessment date etc.) – reference start date + 1 if event is on or after the reference start date;
- The date of the event (visit date, onset date of an event, assessment date etc.) – reference start date if event precedes the reference start date.

Baseline

For safety and efficacy evaluations, the last available assessment (either scheduled or unscheduled) before the first administration of study drug and after the screening visit is defined as “baseline” assessment. If patients have no value prior to first administration of study drug the baseline result will be missing.

Post-baseline

For safety and efficacy evaluations all assessments after the first administration of study drug are defined as “post-baseline” assessment.

Change and percent change from baseline for continuous parameter.

Change from baseline and percent change from baseline will only be summarized for subjects with both baseline and post-baseline values and will be calculated as:

change from baseline = post-baseline value – baseline value

percent change from baseline = $100 * \text{change from baseline} / \text{baseline value}$.

For summary statistics the raw values (and not imputed values) will be used.

Study periods and date of last contact

The overall observation period will be divided into three mutually exclusive segments:

- A screening phase of up to 5 weeks
- A double-blind treatment phase starting with first dose of study drug at Visit 101 and covering 12 weeks of treatment.
- A double-blind treatment withdrawal phase for one week starting after 12 weeks of treatment with Visit 201.

Inferential analysis will be performed on either only treatment phase or on both treatment and treatment withdrawal phase separately. It is never the case that both phases will be pooled together.

Visit windows

Visit windows will be applied for all measurements except NRS scores. The definition of seamless windows can be found in the following [REDACTED] location [REDACTED]

[REDACTED] the most recent version of this document available before the database lock will be used to determine the visit windows for baseline and post baseline visits and treatment discontinuation visit mapping.

[figure not shown]
These visit windows need not to be exactly the same as the formal visit windows what the sites have to follow for their scheduling.

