3.2 Rationale for study design

The study is intended to provide information on the minimum effective dose and the optimal dose range for therapeutic doses of EMA401. It will evaluate the safety and efficacy of three dose levels of EMA401 in the treatment of PHN.

For each dose, the aim is to estimate the treatment effect of the investigational drug (EMA401) compared to placebo, for the target population on the primary pain parameter. The treatment

effect of interest accounts for post-randomization events in a way that reflects their possible relationship to the investigational treatment. In particular, the treatment effect of interest:

- shall not be confounded by events which are deemed non informative on the effect of the study medication, even if they may have the potential to confound it (e.g. some changes in concomitant medications), and
- shall account for events reflecting the unfavorable outcome when patients are unable to continue taking the study medication or unable to benefit from it (such as study treatment discontinuations for specific reasons).

Further details are provided in [Section 9.4.2](#).

The standard methodology for the purpose of establishing evidence of a dose response based on the above treatment effect is to conduct a double-blind, placebo-controlled, randomized, parallel group study. Twelve weeks of exposure is required for assessment of treatment response and registration in chronic pain conditions. The staggered approach to randomizing patients to the EMA401 300 mg b.i.d. arm following DMC unblinded review of safety data, together with clinical assessments every two weeks will ensure patient safety.

The study will evaluate the potential for a rebound effect of EMA401 in both safety and efficacy after study drug discontinuation during a treatment withdrawal period designed to minimize bias.

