2.8 Safety analyses

Safety analyses will be conducted using the safety (SAF) population. Patients will be analysed by the actual treatment they received. All the safety analyses including AEs, vital signs, Laboratory parameters, ECGs [REDACTED] will be reported for double blind treatment period as well as for the treatment withdrawal period separately.

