2.8.3 Laboratory data

The summary of laboratory evaluations will be presented for three groups of laboratory tests: Hematology, Chemistry and Urinalysis.

The number and percentage of patients with newly occurring or worsening laboratory abnormalities meeting the clinically notable criteria at any post-baseline visit will be summarized by laboratory parameter. For a patient to meet the criterion of a newly occurring clinically notable value, the patient needs to have a baseline value that is not clinically notable for that parameter. For a patient to meet the criterion of a worsening clinically notable value, the patient needs to have a baseline value that is clinically notable and also have a worse post-baseline value. For patients with missing baseline value, any post-baseline notable value will be considered as newly occurring.

Incidence of newly occurring liver enzymes abnormalities and renal events will be summarized using the number and percentage of patients by treatment group. Notable laboratory values will be listed.

Laboratory assessments performed at the follow-up visits in the scope of the USM will not be included in the summaries but will be listed. That means, assessments reported 21 days after end of study date will not be included in the summary tables.

Liver function tests (LFT)

To evaluate potential drug-induced liver injury, the number and percentage of patients with newly occurring or worsening abnormalities in liver function tests at any time post-baseline will be summarized by treatment. The same approach as for notable laboratory values will be used to define newly occurring or worsening abnormalities in liver function tests.

When a criterion contains multiple laboratory parameters, the criterion will only be considered to have been met when all conditions occur at the same time (i.e., within the same sample). A case where all criteria are met at a post-baseline time point will be considered as newly occurring if the criteria are not met at baseline and will be considered as worsening if the criteria are met at baseline and at least one component is worsening from baseline irrespective of whether the other(s) are better.

Listings of patients with clinically notable LFT values will be provided.

The same analysis will be repeated for the Treatment withdrawal epoch.

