2.8.4.2 Vital signs

The number and percentage of subjects with clinically notable vital signs will be presented. The same approach as for notable laboratory values will be used to define newly occurring notable vital sign values. Notable vital sign values will be listed.

Notable criteria are:

Variable	Criterion value		Change relative to baseline
Heart rate/pulse	120 bpm 50 bpm	and an and a	increase of ≥ 15 bpm decrease of ≥ 15 bpm
Systolic blood pressure	180 mm Hg 90 mm Hg	and an and a	increase of ≥ 20 mm Hg decrease of ≥ 20 mm Hg
Diastolic blood pressure	105 mm Hg 50 mm Hg	and an and a	increase of ≥ 15 mm Hg decrease of ≥ 15 mm Hg
Weight	Baseline weight (kg)	and an and a	increase of ≥ 7% decrease of ≥ 7%

bpm= beats per minute

Data of subjects with newly occurring notable vital signs abnormalities will be listed in an additional listing.

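### Withdrawal-week tables of newly occurring laboratory, vital-sign and ECG abnormalities use only the pre-treatment baseline, so carry-over is counted and some deterioration after Week 12 goes unflagged

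*SAP*

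**What the plan says.** SAP 2.1.1 (General definitions) gives a single baseline for safety and efficacy: "the last available assessment (either scheduled or unscheduled) before the first administration of study drug and after the screening visit is defined as" baseline. Its companion definition covers everything later: "For safety and efficacy evaluations all assessments after the first administration of study drug are defined as" post-baseline. Values at Visit 199 (Week 12) and Visit 201 (Week 13) are therefore both simply post-baseline.

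SAP 2.8 says that the safety analyses, including laboratory parameters, vital signs and ECGs, "will be reported for double blind treatment period as well as for the treatment withdrawal period separately". The withdrawal tables have five groups: placebo throughout and, for each of the two active doses, continue or switch to placebo.

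SAP 2.8.3 calls a notable value newly occurring if the baseline value was not notable. It calls it worsening if baseline was notable and the later value is worse. The liver-function text there adds: "The same analysis will be repeated for the Treatment withdrawal epoch". SAP 2.8.4.1 applies the same approach to QTc, and SAP 2.8.4.2 does so for vital signs: "The same approach as for notable laboratory values will be used to define newly occurring notable vital sign values". Both sections also have criteria based on change from baseline.

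Protocol 3.2 gives the purpose of the withdrawal week: "The study will evaluate the potential for a rebound effect of EMA401 in both safety and efficacy after study drug discontinuation". SAP section 4 drops the laboratory, vital-sign and ECG-interval summaries other than those of abnormalities, together with the laboratory shift tables and the safety figures.

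**The concern.** The withdrawal week asks what changes once active drug is stopped at Week 12. The tables instead compare Week 13 with the state before the first dose. This can go wrong in two ways. An abnormality that developed during the 12 weeks and has not resolved is reported as arising in the withdrawal week. A patient who improved on treatment and deteriorated after stopping may not meet a change criterion that is measured from before treatment.

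The first case is not remote, because SAP 2.8.1.1 names raised hepatic enzymes as a potential risk of the drug. The second bears directly on rebound. With the other summaries removed, the abnormality tables are the main aggregate view of laboratory, vital-sign and ECG data for that question.

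**Working it through.** The plan states no figure on this point, so there is none to reproduce. The check applies the definitions to example patients and then gives expected counts.

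**Inputs**
- Systolic criterion (SAP 2.8.4.2): value 180 mm Hg, taken as at or above, with a rise of at least 20 from baseline.
- QTcF criterion (SAP 2.8.4.1): above 500 msec, or a rise of more than 60 msec from baseline.
- ALT or AST above 3 × ULN is a listed laboratory abnormality (SAP 5.3).
- 129 patients randomized (SAP, Amendment 1) in a 1:1:1 ratio; active patients split 1:1 into stop or continue (Protocol 3.1).
- Vital signs, hematology and chemistry, urinalysis and ECG are scheduled at both Visit 199 and Visit 201 (Protocol Table 6-1). Weight is not scheduled at Visit 201, so the vital-sign point concerns pulse and blood pressure.

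**Step 1: example patients (values invented for illustration)**

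| Measure | Pre-dose | Week 12 | Week 13 | Change from pre-dose | Change from Week 12 | Under the SAP rule | Against Week 12 |
|---|---|---|---|---|---|---|---|
| Systolic | 140 | 182 | 182 | +42 | 0 | newly occurring | not new |
| Systolic | 165 | 150 | 181 | +16 | +31 | not notable | newly occurring |
| QTcF | 410 | 390 | 455 | +45 | +65 | not notable | newly occurring |

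The first row is carry-over. ALT that is normal before dosing, above 3 × ULN at Week 12 and still above it at Week 13 behaves the same way. The second and third rows are missed deteriorations. Both end above the pre-treatment level, so they would matter even if rebound meant overshoot beyond that level.

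**Step 2: group size**

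129 / 3 = 43 per arm, and 43 / 2 = 21.5, so at most about 21 to 22 per stop or continue group, and fewer after early termination. One carried-over patient adds 1/21 = 4.8 percentage points.

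**Step 3: expected counts**

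Let p be the proportion with a notable abnormality at Week 12 that persists to Week 13 but was absent before dosing. Let q be the proportion of the remaining patients who truly develop one on stopping, and take no new cases in the continue group. Both p and q are assumptions, since the documents give neither.
- Pre-dose baseline: stop = n[p + (1 − p)q]; continue = np.
- Week 12 reference: stop = n(1 − p)q; continue = 0.
- Carry-over share of the stop count = p / [p + (1 − p)q].

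With n = 21 and q = 5%:

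| p | Stop, pre-dose | Continue, pre-dose | Stop, Week 12 reference | Carry-over share |
|---|---|---|---|---|
| 5% | 2.05 | 1.05 | 1.00 | 51% |
| 10% | 3.05 | 2.10 | 0.95 | 69% |
| 20% | 5.04 | 4.20 | 0.84 | 83% |

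With q = 10% the shares are 34%, 53% and 71%. In every row the expected stop-minus-continue difference is the same under both references (for p = 5%, 2.05 − 1.05 = 1.00). Carry-over adds equally to both sides. It masks the contrast but does not shift it.

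**The case against.** The strongest reply is that stop versus continue is randomized within dose and the tables are headed by those groups. Carry-over is then expected equally in both, provided a Week 12 abnormality is as likely to last one more week off drug as on it. That stands: a reader might infer that the contrast is biased, but the documents support only dilution and inflated absolute counts. The placebo-throughout group does not balance carry-over from active drug in this way.

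A second reply is that other outputs remain. Adverse events are reported by epoch, clinically significant findings must be reported as adverse events (Protocol 9.5.2), and notable values are listed, so individual cases can be traced. That also stands. A reader might infer that the rebound question cannot be answered at all, which goes too far.

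Third, rebound is not defined. If it means overshoot beyond the pre-treatment level, the pre-dose baseline is useful. A systolic pressure of 182, then 150, then 181 is only a return to that level and does not show a missed rebound. This is a reason to keep the existing baseline, but it does not cover the second and third rows of the first table.

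Fourth, the SAP refers to a separate visit-window document that is not available here. Nothing in the SAP says that it sets a withdrawal reference. The sentence on repeating the analysis sits in the liver-function text; for the other parameters, withdrawal reporting rests on SAP 2.8.

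Finally, SAP 2.1.1 describes the last phase as "A double-blind treatment withdrawal phase for one week starting after 12 weeks of treatment with Visit 201". Because Table 6-1 puts Visit 201 on Day 92, a reader might infer that the whole withdrawal week falls in the treatment phase. The same sentence says it starts after 12 weeks. SAP 1.1 has completers entering at Visit 199, Table 6-1 footnote 7 starts withdrawal medication that evening, and SAP 2.8.1 uses the Week 12 visit as the boundary. This is an editorial slip.

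**Conclusion.** The point holds in a limited form. For the withdrawal week, the newly occurring and worsening tables count on-treatment abnormalities that are still present at Visit 201, and they miss some deteriorations after Week 12. Absolute counts are inflated by about 5 percentage points per carried-over patient in a group of 21. Over the assumed ranges (p 5% to 20%, q 5% to 10%), carry-over is between 34% and 83% of the stop-group count. On-treatment abnormalities that resolve before Visit 201 do not carry over. A rebound that newly crosses a limit and meets the pre-dose criteria is still counted.

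These are descriptive tables in a trial that ended early, and the adverse-event analyses are not affected in this way. The change is still worth making, because these tables carry most of the aggregate laboratory, vital-sign and ECG information on rebound and the correction needs no new data.

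**What to change.** In SAP 2.1.1, add a withdrawal-epoch reference value: the last assessment on or before Visit 199 and before the first withdrawal-epoch dose. Present the withdrawal-epoch newly occurring and worsening tables for laboratory, liver-function, pulse and blood-pressure, and ECG data against this reference in addition to the pre-treatment baseline. Do not replace the pre-treatment baseline: it shows overshoot beyond the pre-treatment level, and it stays the only reference for the treatment epoch.

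As an editorial correction, state that the withdrawal phase starts after Visit 199 and ends at Visit 201.

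The cost is one extra baseline flag in programming and a second set of small descriptive tables.
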